4.1.2.3.4 Guidelines for the Treatment of Study Drug-induced Skin Toxicity

Skin toxicity is a class-effect observed with PI3Ki/mTORi agents. Close monitoring of potential skin reactions will be performed at each planned visit and will be reported as adverse event. The most frequent skin adverse events reported are: maculopapular rash (only a minority present acneiform rash) (refer to Table 10 for clinical management); pruritus and dry skin. The onset is typically within the first 2 months of treatment start and is reversible with adequate comedication and treatment interruption if needed. Photographs of a skin rash event as well as skin biopsy are recommended, if possible.

According to the investigators discretion, a paired biopsy could be obtained (from both an affected and an unaffected skin area for local histopathology assessment) to further assess rash if clinical appropriate.

Recommended therapies for skin toxicity events (refer to Table 10 for specific guidance according to the type of skin toxicity):

- ◆◆ Topical steroids of moderate potency (face and folds): triamcinolone 0.025%; aclometasone 0.05% (< 8 weeks continuously), for mild and moderate rashes.
- ◆◆ Topical steroids of high potency (trunk/extremities): fluocinonide 0.05%; clobetasol 0.05% cream or spray (< 8 weeks continuously), for mild and moderate rashes.
- ◆◆ Oral antihistamines (sedating, evening): diphenhydramine 25 to 50mg TID; hydroxizine 25mg TID or QID;
- ◆◆ Oral antihistamines (non-sedating, day time): fexofenadine 180mg QD or 60mg TID (monitor the use of this class of drugs since skin toxicity has also been reported)

- •• Oral corticosteroids: prednisone 0.5mg/kg or equivalent up to 5 days of treatment
- •• In case of mild acneiform rashes topical antibiotics: clindamycin 1% to 2%; erythromycin 1% to 2% (gel or solution formulation can be used, ointments cannot be used); metronidazole 1%; silver sulphadiazine.
- ◆◆ For more severe acneiform rashes oral antibiotics: doxycycline 100mg BID; minocycline 100 mg BID; oxytetracycline 500mg BID for 6 weeks can be considered. If infection suspected (yellow crusts, purulent discharge, painful skin/nares), then switch to broad spectrum/gram negative antibiotics; consider skin swab for bacterial culture.
- ◆◆ Topical antiprurities (pramoxine 1%, doxepin 5% cream) applied twice daily
- ♦♦ For severe pruritus GABA Agonists: Gabapentin 300mg every 8 hours, or pregabalin 50 to 75 mg every 8 hours (to adjust of renal impairment) can be considered. Dose should be adjusted depending on patient's clinical condition be of potential and common side effects observed with GABA agonists such as: somnolence, dizziness (both drugs) and peripheral edema (Gabapentin) among others AEs.

Dry skin has been reported, it is recommended that patients with dry skin use mild and fragrance free soaps and detergents. According to the severity and BSA extension patients may apply mild moisturizers, ammonium lactate cream 12% or salicylic acid cream 6% BID.

Photosensitivity has been described in patients although preclinical experiments demonstrated that buparlisib has no potential phototoxic effect. Patients should be advised to take measures to protect themselves from direct exposure to sunlight, including regular use of sunscreen (factor 20 at least), wearing of sunglasses, using of hats, and protective clothes when outdoors.

4.1.2.3.5 Guidelines for the management of Posterior Reversible Encephalopathy Syndrome (PRES)

There have been rare reports of PRES occurring under treatment with buparlisib. Signs and symptoms may include severe headache, confusion or seizures, altered consciousness, visual disturbances, with or without associated high blood pressure. Patients are instructed in the written patient information to inform their treating physician if they suspect such an event. Take appropriate measures in such cases to assess the signs and symptoms. If PRES is suspected based on the signs and symptoms, buparlisib should be interrupted and a brain MRI should be performed to confirm the diagnosis.

4.1.2.3.6 Management of Pneumonitis

Pneumonitis is a known side effect of rapamycin analogues. Based on the literature, the class of PI3K inhibitors has not previously been associated with the development of pneumonitis. Clinically significant pneumonitis typically accompanied by non-specific symptoms including dyspnea, nonproductive cough, fatigue, and fever. Diagnosis is generally suspected in individuals who develop these symptoms or in asymptomatic individuals in whom a routine chest CT scan reveals a new ground glass or alveolar infiltrate.

In ongoing clinical trials with buparlisib in the single agent setting two cases of Pneumonitis occurred. In the study BKM120X2101 one patient experienced pneumonitis

Grade 2 eight weeks after the first dose of buparlisib at 100mg which resolved in 7 days after antibiotic therapy and discontinuation of the study treatment due to fatigue. In the Japanese study BKM120X1101 one case of Pneumonitis occurred in a patient given 100 mg one month after the start of study medication with buparlisib. The patient experienced Pneumonitis with fatal outcome which was concomitant to progression of underlying malignancy including the progression of existing and the appearance of new lesions in combination with increasing pleural effusion (see Buparlisib Investigator Brochure). All patients participating in clinical trials administering buparlisib will be routinely asked about the occurrence of adverse events which could include new or changed pulmonary symptoms (consistent with lung abnormalities). CT scans and pulmonary function test should be done, as clinically indicated, or if there are symptoms that indicate that the patient has developed Pneumonitis. In case of a documented pneumonitis, the guidelines (including dose modifications) in Table 14 should be followed. Consultation with a pulmonologist is highly recommended for any pneumonitis case identified during the study.

Table 14. Management of Pneumonitis

1 abic 14.	Management of 1 neumonitis		
Worst Grade Pneumonitis	Required Investigations	Management of Pneumonitis	Buparlisib Dose Adjustment
Grade 1	CT scans with lung windows. Repeat at least every 8 weeks until return to within normal limits.	No specific therapy is required	Administer 100% of buparlisib dose.
Grade 2	CT scan with lung windows. Consider pulmonary function testing includes: spirometry, DLco, and room air O₂ saturation at rest. Repeat at least every 8 weeks until return to within normal limits. Consider a bronchoscopy with biopsy and / or BAL.	Symptomatic only. Consider corticosteroids if symptoms are troublesome.	Reduce buparlisib dose 50% (see Table 10) until recovery to ≤ Grade 1. Study treatment may also be interrupted if symptoms are troublesome. Patients will discontinue study treatment if they fail to recover to ≤ Grade 1 within 3 weeks.

Grade 3	CT scan with lung windows and pulmonary function testing includes: spirometry, DLco, and room air O ₂ saturation at rest. Repeat at least every 6 weeks until return to within normal limits. Bronchoscopy with biopsy and / or BAL is recommended.	Consider corticosteroids if infective origin is ruled out. Taper as medically indicated.	Hold treatment with buparlisib until recovery to ≤ Grade 1. May restart study treatment within 3 weeks at a 50% dose reduction if evidence of clinical benefit.
Grade 4	CT scan with lung windows and required pulmonary function testing, if possible, includes: spirometry, DLco, and room air O ₂ saturation at rest. Repeat at least every 6 weeks until return to within normal limits. Bronchoscopy with biopsy and / or BAL is recommended if possible.	Consider corticosteroids if infective origin is ruled out. Taper as medically indicated.	Discontinue treatment with buparlisib.

4.1.2.3.7 Management of Liver Toxicities

Monitoring Cycle 1 and 2: **every other week** (if visit schedule allows a more frequent monitoring this should be considered) or more frequently if clinically indicated especially for patients with borderline acceptable AST/ ALT/ bilirubin* values.

Monitoring Cycle 3 and more: monthly or more frequently if clinically indicated. In case of any occurrence of ALT/ AST/ bilirubin* increase \geq Grade 2 the liver function tests must be monitored weekly or more frequently if clinically indicated until resolved to \leq Grade 1.

In case of any occurrence of ALT/ AST/ bilirubin* increase \geq Grade 3 the liver function tests must be monitored weekly or more frequently if clinically indicated until resolved to \leq Grade 1; hereafter the monitoring should be continued every other week or more frequently if clinically indicated until the end of treatment with study medication. Patients who discontinued study treatment should be monitored weekly, including LFTs* or more frequently if clinically indicated until resolved to \leq Grade 1 or stabilization (no CTCAE grade change over 4 weeks).

4.1.2.4 Study discontinuation

All interruptions or changes to study drug administration must be recorded.

It will be documented whether or not each patient completed the clinical study. If for any patient either study treatment or observations were discontinued the reason will be recorded. Reasons that a patient may discontinue participation in a clinical study are considered to constitute one of the following:

- 1. adverse event(s)
- 2. abnormal laboratory value(s)
- 3. abnormal test procedure result(s)
- 4. disease progression
- 5. protocol violation
- 6. subject withdrew consent
- 7. lost to follow-up
- 8. administrative problems
- 9. death

4.2 Treatment Administration

4.2.1 Buparlisib Administration

The study drug buparlisib will be self-administered (by the patients themselves). The investigator will instruct the patient to take the study drug exactly as specified in the protocol. Buparlisib will be administered on a continuous once daily dosing schedule at a dose of **80mg daily**. Patients should be instructed to take the dose of buparlisib with Sonidegib (see below) daily in the morning, two hours after a light breakfast (morning meal) at approximately the same time each day. Buparlisib should be taken with a glass of water and consumed over as short a time as possible. Patients should swallow the capsules as a whole and not chew them. Do not crush capsule. Patients should continue to fast for 2 hours after the administration of each buparlisib dose.

If vomiting occurs during the course of treatment, no re-dosing of the patient is allowed before the next scheduled dose. The occurrence and frequency of any vomiting during a treatment cycle must be noted as an adverse event. If the patient forgets to take her/his dose before 6:00 PM, then the dose should be withheld that day and buparlisib should be restarted the following day.

Patients must avoid consumption of St John's Wort, Seville oranges, grapefruit or grapefruit juice, grapefruit hybrids, pummelos and exotic citrus fruits from 7 days prior to the first dose of study medication and during the entire study treatment period due to potential CYP3A4 interaction with the study medication. Patients must avoid concomitant intake of strong and moderate CYP3A4/5 inhibitors and inducers. Orange juice is allowed. All dosages prescribed and dispensed to the patient and all dose changes during the study must be recorded. If a patient requires a buparlisib dose delay of > 21 days from the previous dose, the patient must be discontinued from treatment completely and will only require a 28-day follow up visit for study completion.

Medication labels will comply with US legal requirements and be printed in English. They will supply no information about the patient. The storage conditions for study drug will be described on the medication label.

4.2.2 Sonidegib Administration

The investigator needs to instruct the patient to take the study drug as per protocol. All dosages prescribed and dispensed to the patient and any dose change or interruption must be recorded in the dosage administration record CRF, as appropriately.

Sonidegib Treatment and Treatment Schedule

Study treatments	Pharmaceutical form and route of administration	Dose	Frequency and/or regimen
Sonidegib	Capsule or tablet for oral use	200 QD	daily

Sonidegib will be administered orally with buparlisib, on a continuous once daily dosing schedule at a dose of 200 mg. Participating patients will receive flat doses on mg/ day basis and not according to their body weight or body surface area. Sonidegib is supplied as 200-mg hard gelatin capsules or tablets. Patients will receive 2 capsules or tablets. The shelf-life and storage conditions will be continually assessed based on accelerated and long term stability data Sonidegib. Medication labels will be in the local language (English) and comply with the legal requirements of USA.

Sonidegib should be taken as follows:

- ◆◆ Patients should be instructed to take their once-a day dose at approximately the same time each day
- ◆◆ Each daily dose of Sonidegib should be taken with a glass of water and consumed over as short a time as possible (eg, 1 capsule every 2 minutes)
- ◆◆ Patients should be instructed to swallow capsules whole and to not chew or open them
- •• Each daily dose of Sonidegib should be taken **2 hours after** a light breakfast (eg, consisting of juice, toast and jam). If breakfast was completed at 08:00 a.m., then study drug administration should occur at 10:00 a.m. Food intake should be avoided for at least 1 hour after study drug administration
- ◆◆ Patients must avoid grapefruit, pomegranate, star fruit and Seville (sour) oranges during the entire study. The juices and products containing these fruits may also be avoided
- •• If vomiting occurs during the course of the treatment, then no re-dosing of the patient is allowed before the next scheduled dose
- •• If the patient forgets to take his/her daily morning dose, then he/she should take Sonidegib within 6 hours after the missed dose. If more than 6 hours have passed, then that day's dose should be omitted and the patient should continue treatment with the next scheduled dose. Patients should inform the investigational site staff of any missed or delayed dose. Clinical drug supply must be accounted for and patients will be asked to return all unused study drug and packaging on a regular basis, at the end of the study or at the time of study drug discontinuation.

At the conclusion of the study, and, as appropriate during the course of the study, the Investigator will return all used and unused study drug, packaging, drug labels, and a copy of the completed drug accountability ledger to Novartis.

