1.5.2.2.4 Clinical safety data on combination of sonidegib plus buparlisib

The combination maximum tolerated dose (MTD) and/or recommended dose expansion (RDE) of sonidegib + buparlisib when co-administered orally, was determined in Study LDE225X2114, an ongoing phase 1b, multi-center, open label, dose escalation study of oral sonidegib in combination with buparlisib in patients with advanced solid tumors (metastatic breast cancer, advanced pancreatic adenocarcinoma, metastatic CRC and recurrent GBM). The RDE was determined based on observed rates of dose limiting toxicities (DLTs) during the first 6 weeks (42 days) of the combination treatment of sonidegib and buparlisib, using a Bayesian Logistic regression Model (BLRM) with Overdose Control (EWOC). The dose escalation phase was completed in December 2013 with 46 patients enrolled across 5 cohorts. The RDE was declared as 400 mg sonidegib QD + 80 mg buparlisib QD.

In a recent randomized double-blind study of sonidegib in patients with locally advanced (La) or metastatic (m) basal-cell carcinoma (BCC), 230 patients were randomized in a 2:1 fashion to receive either 200 mg QD or 800 mg QD of sonidegib. The primary endpoint of objective response rate was met in both arms with both doses achieving meaningful disease control and sustained duration of responses. The 200mg arm had a more favorable risk-benefit profile with respect to toxicities. Therefore, the doses of sonidegib and buparlisib for the current study will be 200mg QD of sonidegib and 80mg QD of buparlisib.

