5.2.2 Sonidegib

Sonidegib will be supplied to the study investigators by Novartis. Sonidegib is formulated in capsules and tablets of 200-mg, strengths. The capsules are packaged in HDPE bottles with a child resistant closure. Sonidegib will be administered orally once a day, as part of each 28-day cycle.

Medication labels will conform to local legal requirements. Patient number will be added by the site pharmacist. The storage conditions for study drug will be described on the medication label. Sonidegib will be dispensed at the start of every cycle, as needed. Sonidegib will be administered orally once a day, as part of each 28-day cycle. The investigational site staff will inform each patient of their actual daily dose, and this will be recorded on the appropriate CRF.

When possible, individual doses will consist of the minimum number of capsules equaling the total dose given the available capsule sizes.

Doses for more than 7 days will be placed at 4₀ and patients will be informed of this at drug dispensing.

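### Section 4.2.2 sets sonidegib at 200 mg once daily but has patients receive two 200-mg units, which is 400 mg

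*Combined protocol and SAP*

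**What the plan says.** Section 1.5.2.2.4 gives the reasoning for the dose. It reports the phase 1b combination study: "The RDE was declared as 400 mg sonidegib QD + 80 mg buparlisib QD". It then turns to a randomized study of 200 mg against 800 mg sonidegib in advanced basal cell carcinoma, where "The 200mg arm had a more favorable risk-benefit profile with respect to toxicities". It concludes that "the doses of sonidegib and buparlisib for the current study will be 200mg QD of sonidegib and 80mg QD of buparlisib".

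Section 4.2.2 carries this forward. Its table lists the sonidegib dose as 200, daily, and its text says the drug is given "on a continuous once daily dosing schedule at a dose of 200 mg". The same paragraph continues: "Sonidegib is supplied as 200-mg hard gelatin capsules or tablets. Patients will receive 2 capsules or tablets".

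Section 5.2.2 gives the same single strength ("Sonidegib is formulated in capsules and tablets of 200-mg, strengths") and adds that, when possible, "individual doses will consist of the minimum number of capsules equaling the total dose given the available capsule sizes". It also says: "The investigational site staff will inform each patient of their actual daily dose, and this will be recorded on the appropriate CRF".

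Section 4.1 and Table 9 direct 50% sonidegib reductions for many toxicities. Section 5.2.1 lists buparlisib in 10-mg and 50-mg capsules.

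**The concern.** The section that investigators and pharmacy follow to dose patients contains two instructions that differ by a factor of two. The wrong one is easy to believe. It equals the phase 1b recommended dose, given with the same 80 mg of buparlisib, and Section 4.2.2 also gives an example of spacing capsules two minutes apart, which suits a multi-capsule dose.

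Following the unit count would give patients double the dose this study chose. Section 1.4.7.2.1 describes exposure as roughly dose-proportional up to 400 mg, so exposure would about double too. Section 1.4.2 describes the muscle toxicity as dose and exposure dependent, and Section 1.4.7.1 says the odds of a dose-limiting CK elevation rise with AUC. With 12 patients per cohort, even a few dosed at 400 mg would mix two regimens in the response rate and safety description.

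**Working it through.** **Main point: daily dose**

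Daily dose = units per dose × strength per unit × doses per day.

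| Input | Value | Source |
|---|---|---|
| Stated dose | 200 mg once daily | 1.5.2.2.4; 4.2.2 table and text |
| Strength per unit | 200 mg | 4.2.2; 5.2.2 |
| Units received | 2 | 4.2.2 |

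- By the unit count: 2 × 200 mg × 1 = 400 mg/day. The stated 200 mg is not reproduced. The ratio is 400 / 200 = 2.0 and the excess is 200 mg/day.
- With one unit: 1 × 200 mg × 1 = 200 mg/day, which agrees with all three dose statements.

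Other readings of the 2:

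- *A smaller unit.* 2 × 100 mg would give 200 mg, but Sections 4.2.2 and 5.2.2 name only 200 mg.
- *A dispensing quantity.* Sections 5.2 and 5.2.2 have drug dispensed at the start of each 28-day cycle. A cycle needs 28 × 1 = 28 units at 200 mg/day, or 28 × 2 = 56 at 400 mg/day, so 2 is not a cycle's supply.
- *One unit of each drug.* The sentence follows directly on the sonidegib supply statement. Buparlisib 80 mg needs 50 + 3 × 10, which is four capsules.

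**Secondary point: the reduced dose, if 200 mg is the starting dose**

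- Sonidegib: 50% × 200 mg = 100 mg = 0.5 of the only listed unit.
- Buparlisib, for comparison: 50% × 80 mg = 40 mg = 4 × 10 mg, which is deliverable.
- Sonidegib from 400 mg, for comparison: 50% × 400 mg = 200 mg = one unit.

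Rows of Table 9 that name a 50% reduction covering sonidegib:

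- No resolution-time condition (6): febrile neutropenia Grade 3; creatinine Grade 3; bilirubin Grade 3; AST/ALT Grade 4; QTc Grade 3 at first occurrence; other adverse events Grade 2.
- Conditional on 7 days (5): neutropenia Grade 3/4 and thrombocytopenia Grade 3/4 (if resolved within 7 days); creatinine 1.5–3 × ULN, bilirubin 1.5–3 × ULN and AST/ALT Grade 3 (if resolution takes longer).
- Total: 6 + 5 = 11. The Grade 2 row for other cardiac events is left out because it names buparlisib only.
- Two more rows (CK Grade 3/4; muscle pain or spasm Grade 3) call for a lower dose without giving its size.

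**The case against.** The strongest case on the other side has four parts.

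1. *Safeguards.* The dose is stated three times as 200 mg, staff must tell each patient the actual daily dose and record it, and drug accountability is required. These limit the consequence and would show what was taken. They do not say which instruction governs.

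2. *400 mg is not known to be unsafe.* It is the declared phase 1b dose with 80 mg buparlisib, and Section 1.4.7.2.1 reports no Grade 3/4 CK elevations below 800 mg on the once-daily schedule. This stands as far as it goes, and no safety signal at 400 mg is claimed here. The reassurance is thin, however. The single-agent study had only 4 patients at 400 mg once daily in Table 1 (5 in Table 3), and 2 patients at 250 mg twice daily had Grade 3/4 CK elevations.

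3. *The strength might be misprinted.* Section 5.2.2 has a stray comma and a plural, and two 100-mg units would also reconcile the text. Nothing in the protocol lists a 100-mg unit for this study, so this is speculation, though cheap to rule out. Similarly, the minimum-number-of-capsules rule gives one unit only if the dose is already taken as 200 mg, so it adds little independent evidence. The three dose statements are enough without it.

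4. *The reduced dose is a detail.* Section 4.1 sends dosing adjustments to discussion with the sponsor, a note to Table 9 allows case-by-case discussion, and the swallow-whole instruction names only capsules. This is accepted: the 100-mg level is unspecified, not impossible, and ranks below the main point.

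**Conclusion.** The concern holds. As written, Section 4.2.2 gives both 200 mg and 400 mg a day, a ratio of 2.0, in intact current text that nothing else corrects. The unit count is the likely error, because 200 mg is stated three times and chosen for a stated reason. That it survives from a 400-mg regimen is plausible but only an inference. The result assumes that 200 mg is the only strength supplied, as the protocol says. The expected doubling of exposure rests on the approximate proportionality reported up to 400 mg.

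The unit count must be corrected. The missing 100-mg delivery method is of lower severity and applies only if 200 mg is the dose. Without it, the reduced level would be settled case by case and could differ between patients.

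**What to change.** **Must be corrected.** In Section 4.2.2, change the unit count to *1 capsule or tablet*. If 400 mg is intended, correct Section 1.5.2.2.4 and the table and text of Section 4.2.2 instead. While making the edit, confirm the supplied strength, state the dose in both mg and units, and drop the capsule-spacing example if the dose is one unit.

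**Lower severity, if 200 mg is kept.** State one deliverable reduced sonidegib level in Table 9 and Section 5.2.2, for example a 100-mg unit or a defined alternate-day 200-mg schedule. These are options for the sponsor to judge; the protocol supports neither at present. Say whether tablets may be split, and use the same level in the two muscle-toxicity rows that give no size.

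**Cost.** The first change is a one-line correction to the protocol and pharmacy wording. The second is an added sentence and possibly a supply decision by the drug supplier. Neither affects sample size or analysis.
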